ICU patients* with an anticipated ICU stay of at least 24 hours, in whom the decision has been made by medical staff to transfuse at least one RBC unit.

*A patient can be included into the study in the Emergency Department if the decision to admit the patient into the ICU has been taken.

Exclusion criteria

- Age younger than 18
- Previous RBC transfusion during the current hospital admission (including transfusion in another hospital for transferred patients)
- Diagnosis of transplantation or hematologic malignancy
- Pregnancy
- Cardiac surgery during the present hospital admission
- Expected to die imminently (<24hrs)
- The treating physician believes it is not in the best interest of the patient to be randomised in this trial.
- Known objection to the administration of human blood products
- Participation in a competing study (see below)

Co-enrolment

- Co-enrolment into any RBC transfusion studies is not permitted
- TRANSFUSE patients cannot be co-enrolled into the POLAR, ARISE, TRISS, and IRONMAN studies.
- Co-enrolment in the ADRENAL, EPO-TBI, PHARLAP, and SPICE studies is permitted by the TRANSFUSE management committee
- Co-enrolment in single site studies is permitted (excluding blood transfusion studies)

STUDY PROCEDURES

Eligible patients

Patients will be screened in the ICU and emergency department for their potential eligibility by the ICU research coordinator (RC) and clinicians. The ICU RC will place a sticker on the patient's chart to assist the ICU team with identifying eligible patients when a blood transfusion is ordered.

Enrolment

The inclusion and exclusion criteria will be checked when a clinical decision is made to transfuse. Transfusion indication, timing and number of the RBC units will be determined by the treating clinicians. However, we recommend following the current ANZ transfusion guidelines for ICU patients [49].

Randomisation

Randomisation will be performed by the ICU research staff using a Web-based computer system.

The patient will be allocated a unique study identification number at randomisation to identify their study involvement for the first and each subsequent RBC transfusion during their hospital stay. This number will be recorded on a sticker placed in the patient's chart and also on the RBC request form sent to the hospital transfusion service. The treatment allocation will be determined using variable block randomisation in a 1:1 ratio, stratified by centre.

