We estimated the baseline mortality using the prospective ANZ observational study data [3]. Over 5 weeks in 2008, 757 patients were recruited. The exclusion criteria of TRANSFUSE leaves 45% recruitable patients. These patients had a hospital mortality of 25% and we conservatively estimate 90-day mortality to be 28%. Our sample size calculation is based on a 15% relative decrease in 90-day mortality, or an absolute decrease of 4.2% from 28% to 23.8%. This effect size would be clinically highly relevant (Number needed to treat to save one life [NNT]=24). This relative decrease is much less than observed in the Koch study (30% RRR) [28], and in our observational study where we found a mortality of 21.3% in the older three quartile versus 13.2% in the freshest quartile (38% RRR) [3]. With a type I error of 0.05 and a type II error of 0.1 (power 90%), the required patient number is 2332 per group. According to our previous studies [54, 55], loss to follow up should not exceed 5%, giving an accurate number of 4898 patients which has been rounded up to 5000 patients.

Statistical and analytical plan

This study will be analysed on an intention-to-treat basis. Analysis will primarily be conducted using SAS version 9.2. (SAS Institute Inc., Cary, NC USA). Baseline comparisons will be performed using chi-square tests for equal proportion, student t-tests for continuously normally distributed variables and Wilcoxon rank sum tests otherwise. The primary outcome, 90 day all-cause mortality will be analysed using a Chi-square test statistic, with results reported as frequencies and percentages per arm. Adjustment for strata (centre) will be made using logistic regression for binomial outcomes and Cox Proportional Hazards regression for time to event data with results reported as Odds Ratios (95% CI) or Hazard ratios (95% CI) respectively. In the unlikely event that baseline imbalances are found to exist between treatment groups, sensitivity analysis will be performed with imbalanced variables included as covariates. A two-sided p-value of 0.05 will be considered to be statistically significant. Additionally a per protocol analysis will be undertaken to account for patients with alloantibodies for whom freshest blood is unavailable. A detailed statistical analysis plan will be published prior to analysis being performed.

Subgroup analyses

A priori subgroup analyses will include:

- Group O versus non group O
- Illness severity according to APACHE III and SOFA scores

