The project aims to address important and unresolved questions regarding potential mechanisms for any adverse effect from the storage age of RBC on patient outcomes. These data will provide detailed measurements of the potential pathways (iron, inflammation, propensity to infection) by which RBCs may produce adverse outcomes in patients. Importantly, by utilising the randomised design of the TRANSFUSE trial, this study will be able to investigate the effect of age of RBCs on these potential pathways. Identification of this mechanism could help future researchers develop specific approaches to preventing these adverse effects. The findings of this project will contribute to the development of strategies to address these effects and inform clinical practice, both in the intensive care and other clinical settings. They will also form the basis for a future potential NHMRC project grant to fund further studies into the mechanisms of adverse effects of transfusion. The collection of patient samples while the TRANSFUSE-trial is recruiting will be an invaluable resource for further research on the mechanisms of adverse effects from RBC transfusion in critically ill patients.

Objectives*Hypothesis*

Transfusion of older RBC compared with freshest available RBC leads to greater extravascular haemolysis and subsequent increase in NTBI resulting in an increase in bacterial growth and inflammation.

Primary Outcome

Indices of increased erythrocyte damage (extravascular haemolysis, iron indices including NTBI and labile plasma iron [LPI]) at 4-hour and 24-hours post the first RBC.

Secondary Outcomes

Bacterial growth in plasma at 4-hour and 24-hours post the first RBC.

Inflammatory cytokines at 4-hour and 24-hours post the first RBC transfusion

Leucocyte adhesion at 4-hour and 24-hours post the first RBC transfusion

Study Design

A sub study of patients enrolled in the TRANSFUSE randomised control trial.

Recruiting Site

The Alfred Hospital Melbourne, the Austin Hospital Melbourne and Monash Medical Centre Melbourne

Inclusion criteria

- Patients randomised in the TRANSFUSE trial and who are going to receive their first RBC transfusion in the current admission in ICU

Exclusion Criteria

- Current therapy with iron supplementation or iron chelation.

Ethics and consent

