Appropriate Human Research and Ethics Committee (HREC) approval and Research Governance, including the use of opt-out consent has been obtained for the TRANSFUSE trial at each participating site. Application for an amendment will be made to the HREC to approve the inclusion of this study. Prospective consent will be obtained from the patient or the person responsible in the first instance, and if this is not possible telephone consent will be sought. If no person responsible is contactable after reasonable attempts, patients will be enrolled under section 42T.

Researchers will ensure that the requirements for section 42T are met before proceeding –

- Patient will not regain capacity within a reasonable time
- The person responsible cannot be ascertained or contacted despite making reasonable efforts
- The medical research procedure is not contrary to the person's best interests
- The medical research procedure is not against the wishes of the person
- The HREC has agreed that the procedure may proceed for a person where that person or their person responsible is unable to consent
- The purpose of the research is to test the effectiveness of the proposed therapy
- The procedure poses no greater risk than the risk inherent in the person's condition and alternative treatment
- The researcher must tell the patient or their person responsible of the medical research procedure once the patient has regained capacity or the person responsible has been ascertained or located and that they are advised that they may withdraw from the treatment.

A copy of the section 42T form will be submitted to the HREC and also to the Office of the Public Advocate.

[figure not shown]
Patients and the person responsible (if applicable) will be given the plain language and information form including details about the study design, methodology and significance.

Research plan and Methods

One hundred and fifty patients will be included in this sub-study. Wherever possible eligible patients will be enrolled consecutively.

After randomisation in the TRANSFUSE-trial, a sample of 18 ml (3 1/2 teaspoons) of blood will be taken before the first RBC unit, at 4 and 24 hours after the transfusion episode.

Figure. Study procedures

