Patient and transfusion data: will be routinely collected as part of the data collected for the TRANSFUSE-trial. Dates and times when samples are taken and results of the experiments performed in the study sites will be recorded in a separate case report form (CRF).

Blood samples: Blood samples (2 x5 ml in lithium heparin tube, 1 x K2E 3ml EDTA (lilac top) tube and 1 x 5 ml in gel lithium heparin) will be sent immediately to the pathology lab of each hospital where plasma samples will be aliquoted and stored at - 80°C before transfer to the Australian Red Cross Blood Service Melbourne Processing Centre (MPC), where they will be stored until recruitment is complete and experiments are performed. For further details refer to the section below “blood sample schedule.”

Experiments:

- Bilirubin, free haemoglobin, haptoglobin, ferritin, serum iron, transferrin and transferrin saturation will be performed in each pathology laboratory at the 3 participating centres.
- The other experiments will be performed at a later date once all patients have been enrolled and samples collected. These experiments are outlined below:
 - i) Non transferrin bound iron (NTBI) and labile plasma iron (LPI, a fraction of NTBI that is redox active) will be measured by FeROS eLPI and LPI assays (Aferrix, Israel), and serum hepcidin will be measured using a commercially available ELISA (DRG, Germany).
 - ii) Bacterial growth will be performed in plasma before and after transfusion without and with desferrioxamine as described elsewhere [64].
 - iii) Inflammatory biomarkers: sCD106 (VCAM-1), sCD62L, sCD62P, ICAM-1, MCP-1, MIP-1a, MIP-1 β , IL-1 α , IP-10, IL-6, IL-8, IL-10, IL-12, IL-4, IL-13, IL-17, IL-21, IFN- γ and IFN- α , will be assessed in plasma samples via multiplex Cytometric Bead Array (BD Biosciences).
 - iv) Leucocyte adhesion

Blood samples schedule

Samples will be taken within 1 hour prior to transfusion (T0), 4 hours after transfusion initiation (T4) and 24 hours after transfusion initiation. For example, if the first RBC transfusion starts at 10 am, the samples T0 will be taken between 9 am and 9.59 am, at 2 pm (samples T4) and at 10 am the following day (samples T24).

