T24 Sample	24 hours after transfusion initiation*	1x5ml lithium heparin tube	Processed in laboratory for immediate analysis as per laboratory protocol	Iron studies: ferritin, transferrin, transferrin saturation, serum iron Haptoglobin
		1 x5ml gel lithium heparin tube	Processed in laboratory for immediate analysis as per laboratory protocol	Free haemoglobin
		1 x5ml lithium heparin	^Centrifuge and aliquot for -80 degrees Celsius storage into: Plasma in heparin, (5 tubes of 0.5ml)	Non-transferrin bound iron Labile plasma iron Hepcidin Bacterial growth
		1 x3ml EDTA tube	^Centrifuge and aliquot for -80 degrees Celsius storage into: Plasma in EDTA, (2 tubes of 0.5ml)	Inflammatory biomarkers (as listed above)

*In the event that multiple RBC units are transfused in the transfusion episode, samples will still be taken 4 hours after initiation of the first RBC transfusion

^Centrifugation will be performed at 16 degrees for 10 minutes with a speed of 2898 G

Data analysis and statistics

Sample size: 150 patients. Enrolment of 150 patients will enable detection of a difference in NTBI at 4 hours of 2.2uM with SD of 3.7 (similar to that shown in healthy volunteers in the study by Hod et al., Blood 2011 [62]),

between patients receiving fresh and older RBC units, accounting for a 20% incomplete data collection rate (which is expected due to the complex management requirements of patients enrolled in this study). Recruitment of 150 patients prior to the completion of the TRANSFUSE-trial (anticipated 18-months from commencement of the sub-study) is feasible based on the 3 centre's current combined recruitment rate of approximately 8 patients per month within usual working hours.

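### The iron substudy is sized for one test (NTBI at 4 hours), but its primary outcome is an undelimited set of indices at two time points with no lead endpoint or multiplicity rule

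*Combined protocol and SAP*

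**What the plan says.** **Primary outcome.** Appendix 3, Objectives, gives "Indices of increased erythrocyte damage (extravascular haemolysis, iron indices including NTBI and labile plasma iron [LPI]) at 4-hour and 24-hours post the first RBC". This is plural, the iron indices are introduced by the word including, and extravascular haemolysis has no marker attached.

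**What is measured.** Under Experiments, the site laboratories measure "Bilirubin, free haemoglobin, haptoglobin, ferritin, serum iron, transferrin and transferrin saturation". NTBI, LPI and hepcidin are assayed later, once enrolment is complete. No section says which of these markers belong to the primary outcome.

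**Sizing.** Data analysis and statistics states: "Enrolment of 150 patients will enable detection of a difference in NTBI at 4 hours of 2.2uM with SD of 3.7", "accounting for a 20% incomplete data collection rate". Appendix 3 gives neither alpha nor power.

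**Analysis.** The Statistical analysis paragraph plans between-group comparisons both of post-transfusion values and of pre-to-post differences. Each is to be made by randomised arm and again by a 14-day split of RBC age. It adds paired before/after tests, correlations with severity and a subgroup by SOFA score. It names no lead marker, lead time point, hierarchy, composite or multiplicity adjustment, and gives no rule for calling the primary outcome positive.

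**The concern.** A primary outcome should tell the reader which single result, or which prespecified combination, decides the question. Here the sizing supports one comparison, while the outcome definition covers at least NTBI, LPI and some measure of haemolysis, each at 4 and 24 hours. If several of these are tested at the usual level and one is significant, nothing in Appendix 3 stops it being reported as a positive primary outcome. The stated ability to detect a difference belongs to one endpoint, whereas the false-positive risk belongs to the whole set.

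At stake is the credibility of the substudy's main finding. The Significance section expects the results to inform practice and to support a later grant application, so a selectively chosen primary result could mislead both uses.

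**Working it through.** **Inputs**
- Difference 2.2 uM, SD 3.7, NTBI at 4 hours (Appendix 3, Sample size).
- N = 150 with 20% incomplete data (same place), so 150 × 0.8 = 120 evaluable.
- Allocation from the main protocol, Randomisation: "variable block randomisation in a 1:1 ratio, stratified by centre". Hence about 60 evaluable per group.
- Alpha and power are not in Appendix 3. Two-sided 0.05 and 90% are borrowed from the main trial's Statistical Considerations, as an assumption.
- Correlations between the test statistics are not in the documents. A range of 0 to 0.9 is assumed.

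**Step 1: reproduce the plan's figure.** For two means, n per group = 2(z_alpha/2 + z_power)² × (SD/difference)².

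2 × (1.960 + 1.282)² × (3.7/2.2)² = 2 × 10.51 × 2.829 = 59.4, so 60 per group and 120 in total. Then 120/0.8 = 150, an exact match. With 80% power the same route gives 45 per group, 90 in total and 113 after inflation, so 90% is the likelier input. With 60 per group the power is Φ(3.257 − 1.960) = 90.3% (89.8% by noncentral t). The arithmetic is sound, and it is the arithmetic of one test.

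**Step 2: count the tests that follow most directly from the outcome wording.**
- NTBI and LPI at two times: 4 tests.
- Adding one haemolysis marker at two times: 6 tests.

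**Step 3: chance of at least one p < 0.05 with no true effect.** If independent, this is 1 − 0.95^m: 1 − 0.95⁴ = 18.5% and 1 − 0.95⁶ = 26.5%. Correlated tests were simulated as equally correlated normal statistics (400,000 draws):

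| Pairwise correlation | 4 tests | 6 tests |
|---|---|---|
| 0 | 18.5% | 26.5% |
| 0.3 | 17.4% | 24.0% |
| 0.5 | 15.6% | 20.7% |
| 0.7 | 13.0% | 16.4% |
| 0.8 | 11.4% | 13.9% |
| 0.9 | 9.4% | 10.9% |

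No cell falls to 5%. These counts use one form of comparison and one grouping. The planned value-versus-change and arm-versus-14-day analyses would add further chances.

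**Step 4: what keeping the set would cost.** With Bonferroni over 4 tests (alpha 0.0125), power for the stated NTBI effect at 60 per group is 77.6%; restoring 90% needs 81 per group, and 162/0.8 gives 203 patients. Over 6 tests (alpha 0.0083), power is 73.2%; restoring 90% needs 87 per group, and 174/0.8 gives 218 patients.

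**The case against.** **The lead endpoint is evident.** The sizing uses NTBI at 4 hours, and the hypothesis sets out a chain from haemolysis through NTBI to bacterial growth and inflammation. An isolated, out-of-sequence change would not support that chain. This has weight. A reader might infer that the plan lets any significant index be declared the primary result, or that the investigators mean to do so. The documents do not say that one significant result counts as success; they only fail to exclude it. Equally, neither the sizing nor the hypothesis declares a lead endpoint, and the hypothesis puts haemolysis beside NTBI.

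**The markers are correlated.** This stands. LPI is described as a fraction of NTBI, and each marker is measured twice in the same patient, so zero correlation is an upper bound rather than a realistic case. Even at 0.9 the risk is about twice the nominal 5%.

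**The number of tests is uncertain.** A reader might count nine laboratory markers at two times, 18 tests, and quote 1 − 0.95¹⁸ = 60% (15% at correlation 0.9). No section assigns that panel to the primary outcome. The lists also differ: bilirubin is under Experiments but missing from the sample table's tests, while hepcidin appears in both. The risk rises as more of the panel is counted, but the 18-test figure is not a finding about this plan.

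**Sampling times.** A reader might also infer that the sampling clock is contradictory, because Research plan and Methods puts samples "at 4 and 24 hours after the transfusion episode". The Blood samples schedule counts from the start of transfusion with a worked clock example, and the table footnote settles episodes with several units by using the first. One loose phrase remains.

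**It is a mechanistic substudy.** True. It is analysed separately and cannot affect the 90-day mortality result, which limits the priority. It still labels a primary outcome and sizes the study for one of its components.

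**Conclusion.** The concern holds in a limited form. The primary outcome is not delimited by marker or time and has no lead endpoint or multiplicity rule, while the sample size supports a single test. The plan therefore leaves room for a positive primary claim based on one chance result.

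The false-positive chance is about 9% to 19% for four tests and 11% to 26% for six. This rests on three assumptions: each test at two-sided 0.05, no true effect, and equal pairwise correlations between 0.9 and 0. The sample-size calculation itself is not at fault. The change is worth making, but it concerns the substudy only.

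**What to change.** In Appendix 3:

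1. Name NTBI at T4 (4 hours after initiation of the first RBC transfusion), compared by randomised arm, as the single primary outcome.
2. Fix one form of that comparison in advance, for example the T4 value adjusted for T0. Without this, the post-transfusion value and the change would remain as two candidate primary tests.
3. List NTBI at T24, LPI and the haemolysis indices as secondary.
4. State the alpha and power behind the 150. Two-sided 0.05 and 90% reproduce it; the authors should confirm that these were the values used.
5. Editorial only: align the timing phrase in Research plan and Methods with the initiation-based sample schedule.

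The cost is wording. No patients, samples or assays are added, and the 150 keeps about 90% power for the named endpoint under the assumed alpha. NTBI is assayed only after enrolment ends, so the choice can be fixed before any NTBI result exists. The small downside is that LPI and the haemolysis indices can no longer be called primary. If the authors want haemolysis kept in the primary set, co-primary outcomes with a stated correction or a fixed testing order would also close the gap. Under Bonferroni, 90% power for the NTBI effect would need 203 patients (four tests) or 218 (six tests).

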Statistical analysis: Data collected for the sub-study will be treated and analysed separately after the TRANSFUSE RCT has been completed. Data will be transformed when skewed and analysis performed on log-transformed values. Parameters before and after the transfusion episode will be compared for each patient using paired t-test. Biological parameters post-transfusion, as well as differences between pre- and post-transfusion values, will be compared according to RBC storage duration category, which will be defined according to the RCT (i.e.: freshest available vs. standard issue) and also according to whether patients were transfused with only RBC younger than 14 days vs. patients transfused with RBC older than 14 days. A correlation between patient severity at randomisation and each parameter (including: post-transfusion extravascular haemolysis and NTBI) will also be performed. A sub group analysis will be performed on the most severe patients according to their SOFA score on the day of transfusion.

Safety

As per the TRANSFUSE trial. There are no additional risks posed by the IT TRANSFUSE sub-study. The results of the study will be forwarded to the Data and Safety Monitoring Committee (DSMC).

Funding

This study is collaboration with the Australian Red Cross Blood Service, who has provided funding for the costs for research staff time, sample collection, processing and testing in addition to in kind support provided by the Blood Service.

Publication

The study will be conducted in the name of Monash University on behalf of the TRANSFUSE investigators. Authorship will be under the names of the sub-study investigators on behalf of the TRANSFUSE investigators. Publication of results will be embargoed until publication of the main study results unless specific permission for early publication is given by the TRANSFUSE management committee.

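### The iron substudy plans two unranked between-arm comparisons per marker and time point, and neither adjusts for the scheduled T0 sample

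*Combined protocol and SAP*

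**What the plan says.** Appendix 3 schedules a baseline draw and two later draws: "Samples will be taken within 1 hour prior to transfusion (T0), 4 hours after transfusion initiation (T4) and 24 hours after transfusion initiation". The sampling table lists the same assays at all three times. The T0 draw follows randomisation but precedes the first study unit, so the allocated blood cannot have affected it.

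For the comparison between storage groups, the statistical analysis paragraph says: "Biological parameters post-transfusion, as well as differences between pre- and post-transfusion values, will be compared according to RBC storage duration category". The groups are defined first by randomised arm and then again by a 14-day cut on the age of the units received. Within patients, "Parameters before and after the transfusion episode will be compared for each patient using paired t-test". Skewed data are to be log-transformed. The paragraph names no model with T0 as a covariate, does not say which between-group comparison is the main one, and gives no multiplicity rule.

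The sample size paragraph is based on "detection of a difference in NTBI at 4 hours of 2.2uM with SD of 3.7", "accounting for a 20% incomplete data collection rate". It does not say whether 3.7 is the SD of the 4-hour value or of the change from T0, and it states neither alpha nor power.

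**The concern.** The substudy hypothesis is a contrast between older and freshest available blood. For that contrast, each marker and time point gets two tests of the same question. One ignores T0 and the other subtracts it in full. If the arms differ by chance at T0, the two estimates move apart, and the plan does not say which one stands.

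Neither test is the efficient use of T0. The post-value comparison leaves in the variance that T0 could explain. The change score adds the noise of the T0 measurement, which hurts when T0 and the later value are weakly correlated. With about 60 evaluable patients per arm, precision matters, and the T0 sample is already in the schedule.

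**Working it through.** **Inputs.** From Appendix 3: 150 enrolled, difference 2.2 uM, SD 3.7, 20% incomplete data. From the main protocol: 1:1 allocation (Randomisation); two-sided 0.05 and 90% power (Statistical considerations), assumed here for the substudy. Not in the documents, so assumed: the correlation rho between T0 and the 4-hour value (0.3, 0.5, 0.7), and k, the ratio of the T0 SD to the 4-hour SD (1 in the main calculation).

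**Step 1: reproduce the 150.** Per arm, n = 2 x (1.960 + 1.282)^2 x (3.7/2.2)^2 = 59.4, rounded up to 60. Total 120, and 120/(1 - 0.20) = 150, an exact match. At 80% power the same route gives 45 per arm and 113 enrolled, which does not match. So the 150 fits an unadjusted two-sample comparison at 90% power and takes no credit for T0. The t-test power at 60 per arm is 89.8%.

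**Step 2: variances relative to the post-value comparison.**
- Post value: 1
- Change score: 1 + k^2 - 2 x rho x k, which is 2(1 - rho) when k = 1
- ANCOVA on T0: 1 - rho^2 (large-sample)

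ANCOVA is never larger than the first, because rho^2 >= 0. It is never larger than the second, because the difference is (k - rho)^2 >= 0. The change score is noisier than the post value when rho < k/2, that is, below 0.5 when k = 1.

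**Step 3: power at 60 per arm** (t-test, SD 3.7 times the square root of the variance factor, k = 1, 3.7 taken as the post-value SD, raw scale).

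| rho | Factor: change | Factor: ANCOVA | Post | Change | ANCOVA |
|---|---|---|---|---|---|
| 0.3 | 1.40 | 0.91 | 89.8% | 77.9% | 92.3% |
| 0.5 | 1.00 | 0.75 | 89.8% | 89.8% | 96.2% |
| 0.7 | 0.60 | 0.51 | 89.8% | 98.6% | 99.5% |

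At rho 0.5, ANCOVA would need 59.4 x 0.75 = 44.6, so 45 per arm, or 90/0.8 = 113 enrolled, for the power that 150 buys without T0.

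**Step 4: how far the change-score figures depend on the assumptions.** At rho 0.3, k = 0.75 gives a factor of 1 + 0.5625 - 0.45 = 1.1125 and power of 86%; k = 0.5 gives 1 + 0.25 - 0.30 = 0.95 and 91%. ANCOVA stays at 92%. If instead 3.7 is the SD of the change, the change score has 90% power at every rho. With k = 1 the post-value SD is then 3.7 / sqrt(2(1 - rho)), and ANCOVA has 98%, 96% and 94% power at rho 0.3, 0.5 and 0.7.

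**Step 5: the unranked pair.** With k = 1, the two test statistics have correlation sqrt((1 - rho)/2). If a result at 0.05 on either test were read as positive, the type I error for one marker, one time point and one grouping would be 8.3% at rho 0, 9.1% at 0.5 and 9.6% at 0.9. Two measures, two time points and two groupings give up to 2 x 2 x 2 = 8 between-group tests per marker.

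**The case against.** Both planned tests are unbiased for the randomised comparison, and this is a mechanistic substudy that cannot affect the 90-day mortality result. That is so, and it limits the weight of the point.

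A reader might infer that planned power is lost or that 150 is too few. The documents do not support this. If 3.7 is the post-value SD, the post-value test keeps its 90%. If it is the SD of the change, the change score does. A shortfall arises only for the change score, under low correlation and similar spread at T0 and 4 hours. Equal spread cannot be presumed, since the hypothesis is that transfusion raises NTBI.

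A reader might also fault the paired t-tests for not comparing arms. That would be misplaced: Appendix 3 aims first to describe changes after transfusion, and a within-patient test answers that aim.

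Nor is the adjusted model free of cost. A T0 draw is scheduled for everyone, but a fifth of patients are expected to have incomplete data. A post-value test keeps a patient who lacks only T0; ANCOVA drops that patient unless a rule is stated. T0 and three centres also use 3 of 118 residual degrees of freedom, about 2.5% of the information, so below a rho of about sqrt(3/118) = 0.16 the model gains nothing unless centre itself explains variance.

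Finally, the 14-day grouping is not randomised. Change scores and ANCOVA can estimate different things there, and the precision argument does not carry over.

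**Conclusion.** The point stands as one of efficiency and clarity for the randomised comparison. Appendix 3 leaves two between-arm analyses unranked and uses T0 in neither as a covariate, and nothing elsewhere in the documents supplies this for the iron substudy. The regression with covariates in Appendix 4 belongs to the renal substudy.

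The direction of the gain is firm in large samples; its size is not. Against the post-value test it is about 2 percentage points of power at rho 0.3, 6 at 0.5 and 10 at 0.7. Against the change score it is about 14, 6 and 1. These figures rest on an assumed rho, equal SDs, 3.7 as the post-value SD, the raw scale although skewed markers will be logged, and an alpha borrowed from the main trial. The 8 to 10% type I error applies only if either test may carry the claim, which the plan neither says nor rules out. The sample size needs no change.

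**What to change.** For the randomised comparison, make the main analysis of each marker and time point a linear model of the post-transfusion value (log scale where skewed) on randomised arm, the T0 value on the same scale, and centre. Name NTBI at 4 hours, the sample-size variable, as the primary test. Label the post-only comparison, the change-score comparison and the 14-day grouping as supportive. Keep the paired t-tests for the within-patient aim.

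State alpha and power in Appendix 3, and say which quantity the SD of 3.7 describes. Add a rule for patients with a post value but no T0, for example imputing the overall mean T0 on the analysis scale without regard to arm.

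The cost is a few sentences and a few degrees of freedom. No extra samples or patients are needed. The substudy is to be analysed only after the main trial has been completed, so the wording can be settled before the data are examined.
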